**2) Objectives**

The purpose of this study is to evaluate the efficacy of breast computed tomography (CT) for breast cancer detection. A breast CT scanner has been built using a flat panel detector and cone beam techniques. The breast CT system will be evaluated to determine the efficacy of the scanner in the detection of lesions and the results will be compared to breast MRI, mammography and the histopathological findings of the detected lesions.

We have studied the potential of breast CT (bCT) for breast imaging under an NIH-funded Biomedical Research Partnership (BRP) grant (R01 EB002138-10), and 4 breast CT scanners have been developed that have imaged over 600 women to date (under more than one IRB-approved protocol). The BRP grant cannot be renewed, and with this (resubmitted) R01 grant application, we seek to finalize our research in breast CT – The specific aims have been significantly modified as a result of the first critique, and we now focus on a narrower set of remaining issues.

Specific Aims:

Contrast injections are used to identify breast cancer lesions in clinical procedures, most notably breast MRI (gadolinium contrast agent). Other investigators have demonstrated the utility of iodine contrast agent injection for breast cancer delineation in projection mammography techniques, using both dual energy subtraction (Lewin) and temporal subtraction (Yaffe) to highlight the visualization of the breast tumor.

Specific Aim 1: Develop scatter correction and image processing methods to improve Hounsfield Unit (HU) accuracy.

The UC Davis bCT scanners do not use an anti-scatter grid to keep radiation dose low. We have developed an inverse beam stop method for accurate scatter-correction, but this needs to be implemented in software. In addition to this physics-based scatter correction method, additional image processing methods will be explored to maximize the quantitative integrity (Hounsfield unit accuracy) of bCT images while minimizing cupping. We hypothesize that improvements in HU

accuracy will improve the quantitative predictive value of CE-bCT, for example, comparing differences in lesion HU before and after contrast injection ( $\Delta$ HU).

**Specific Aim 2: Optimize non-contrast bCT imaging for microcalcification detection.** The ultimate goal of the breast tomography project is to improve breast cancer screening beyond the limitations of projection mammography, and for practical reasons this precludes contrast injection for screening normal risk patients. Since the (4th) Doheny scanner has >4 times the MTF (at 10%) than earlier scanners, we believe that bCT can now compete with mammography for microcalcification detection. In this aim, image optimization in terms of microcalcification detection performance will be performed. Using physical phantoms with microcalcifications, image reconstruction parameters (apodization filter, matrix dimensions, preprocessing techniques, etc.) will be optimized and evaluated using mathematical metrics and human observer performance studies on phantoms containing microcalcifications.

**Specific Aim 3: Clinical Trial: Imaging women using breast CT and CE-MRI**  
Women with suspicious lesions (BIRADS 4+5) will undergo digital mammography ("2D") and tomosynthesis ("3D") as standard of care workup. Patients who participate will undergo both unenhanced and contrast enhanced breast CT imaging, and also contrast-enhanced breast MRI. Both breasts (affected and unaffected) will be imaged with bCT and MRI. Our facility biopsies 2400 patients over 5 years, and power analysis shows that we will need a total of 400 patients whose images will be used for the normal-risk patient screening comparisons (Aim 4) and for the high risk patient screening comparisons (Aim 5).

**Specific Aim 4: Normal Risk Screening Performance: Comparison of non-contrast bCT with 2D and 2D+3D mammography.** The 4th bCT scanner ("Doheny") is now operational and has four times the spatial resolution of our earliest scanner. Non-contrast bCT has demonstrated better mass-lesion detection performance than mammography (Lindfors, et al, 2008) but using the earlier bCT systems, microcalcification detection was inferior to mammography. Doheny now has vastly improved spatial resolution, and we hypothesize that bCT is (now) equal to or better than screening mammography for microcalcification detection. In this aim, digital mammography and non-contrast bCT images will be compared in a standard receiver operating characteristic (ROC) study. Mammography with Tomosynthesis will also be compared against non-contrast bCT, using ROC methods. A full-search methodology will be used.

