**Specific Aim 5: High Risk Screening Performance: CE breast CT and CE-breast MRI.**  
To evaluate the potential of CE-bCT for use in high risk screening (as MRI is used now), CE-bCT ROC performance will be compared against CE-MRI ROC performance. Radiologists will perform full 3D search of the CT and MRI (independently) volume data sets (both with and without contrast) and report

overall probability of malignancy for each modality. Location-specific metrics for potential FROC or LROC analysis will also be captured. Assessment of  $\Delta$ HU will also be performed to quantitatively evaluate predictive performance for malignancy.

Specific Aims 1 and 2 do not require changes in hardware; these two aims are completely focused on post-acquisition image processing techniques (software). Therefore, accrual to the clinical trials as described in Aim 3 can commence on day one of this project. The acquired projection image data from the scanner is always saved, and once the scatter-correction and flat fielding techniques (Aim 1) and optimized reconstruction methods (Aim 2) are finalized, images will be re-reconstructed and become available for the ROC studies on normal-risk screening (Aim 4) and high-risk screening (Aim 5) performance. We believe that this 5 year study will demonstrate that non-contrast bCT can outperform 2D & 3D mammography in breast cancer screening for normal risk patients, and that CE-bCT is (at least) equivalent to CE-MRI for screening high-risk women.

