### Summary of Initial Experience

Dedicated breast computed tomography (bCT) is a fully tomographic cone beam x-ray based imaging modality that generates three dimensional images of the breast. In initial clinical trials, bCT was shown to provide significantly better visualization of mass lesions than that capable with mammography; however mammography outperformed bCT in visualizing microcalcifications.[1] Further work using injected iodine based contrast medium in conjunction with bCT, or so called contrast-enhanced bCT (CE-bCT), verified that mass lesions are seen better on CE-bCT than on mammography. However, the visualization of microcalcifications, specifically those associated with a malignant lesion, was similar at CE-bCT and mammography, suggesting that the use of iodine contrast medium may close the gap between bCT and mammography in visualizing malignancy.[2] Due to the contrast injection, CE-bCT is a more invasive procedure than mammography and may not be appropriate as a modality for breast cancer screening in the general population. CE-bCT may have more potential as a tool for screening in high risk patients, for cancer staging, and for tumor targeting. Unenhanced bCT may still serve as an important imaging modality for tumor staging and targeting in patients with contraindications to iodine contrast imaging.

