**6) Study Endpoints**

**Primary:** The primary study endpoint will be the assessment of patient safety and comfort at the conclusion of the imaging phase of the study.

**Secondary:** The secondary study endpoint will be the comparison of breast MRI versus breast CT in terms of sensitivity and specificity using biopsy findings as the standard of truth for lesion characterization. True positives & negatives and false positive & negatives will be defined and ROC (receiver operating characteristics) curves will be generated.

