## **8) Data and/or Specimen Management and Confidentiality**

Statistics and Determination of Study Sample and Data Analysis:

For this next cohort of 400 subjects, the following statistical analysis has been performed:

Over the past three years, the UC Davis breast imaging facility has averaged 15,818 screens, 2,665 diagnostic exams, and 480 biopsies annually. Patient recruitment will be ongoing during the first 4 years of the proposal, so that a “forgetting” time of at least 6 months can be enforced from the time of imaging to the reader studies. All cases will be recruited from BIRADS 4 & 5 women who will be biopsied in our facility, and we assume the historical 38% positive biopsy rate for our facility. The recruited women will undergo pre- and post- contrast bCT imaging, as well as pre- and post- contrast CE-MRI imaging. These women will all have had bilateral 2D and 3D mammography imaging as part of their screening and diagnostic workup. The biopsy findings will serve as ground truth for all cases. In addition, the vast majority of women will have all findings limited to a single breast, leaving the unaffected breast available as a non-cancer image (i.e. normal) for the screening study in Aim 4. Based on the power studies described below, the minimum number of women we need to recruit to run the study is 150 with biopsy-verified cancer and an additional 50 with benign findings (i.e.,  $150 / 0.38 = 395 \approx 400$ ). At a minimum, we plan to recruit 400 and will strive to recruit substantially more. Given a total of 1,920 candidate women, the 38% positive rate for biopsy, and a 25% rate of recruitment, we would expect to be able to acquire 182 cases ( $1920 \times 0.38 \times 0.25$ ) with cancer over the recruitment period, and this would correspond to  $\sim 298$  ( $1920 \times 0.25 \times [1-0.38]$ ) women with benign findings.

These recruitment figures are conservative in terms of the recruitment rate, and they still provide more than enough cases for our studies.

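### Aim 4 states a microcalcification hypothesis, but its only patient analysis is an overall ROC comparison that does not answer it

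*Combined protocol and SAP*

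**What the plan says.** Specific Aim 4 (section 2, Objectives) is headed as a comparison of screening performance between non-contrast bCT and 2D and 2D+3D mammography. It recalls that "Non-contrast bCT has demonstrated better mass-lesion detection performance than mammography", says that the earlier scanners did worse on microcalcifications, points to the new scanner's resolution, and then states: "we hypothesize that bCT is (now) equal to or better than screening mammography for microcalcification detection".

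The analysis follows directly: "In this aim, digital mammography and non-contrast bCT images will be compared in a standard receiver operating characteristic (ROC) study". A second ROC comparison, against mammography with tomosynthesis, is added. Both use full search, and neither is restricted or broken down by lesion type.

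Section 8 draws the cases without regard to lesion type: "All cases will be recruited from BIRADS 4 & 5 women who will be biopsied in our facility". Biopsy is the truth standard. The paragraph on numbers of patients sizes Aim 4 on 4 readers, AUC 0.825 versus 0.875, and 82% power with 150 positives and 250 negatives. The closing paragraph of the aims expects that "non-contrast bCT can outperform 2D & 3D mammography in breast cancer screening for normal risk patients".

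**The concern.** The one sentence in Aim 4 worded as a hypothesis concerns microcalcifications, while the analysis concerns cancers of every type together. The direction differs too: the hypothesis is of the equal-or-better kind, whereas Aim 4 is sized for an improvement and gives no margin.

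The background makes the gap matter. In the initial trials "mammography outperformed bCT in visualizing microcalcifications", while masses were seen better on bCT. Effects that run in opposite directions are the situation in which a pooled AUC can hide one of them. Aim 4 could therefore succeed on its overall AUC while its stated hypothesis is false, and nothing in the planned analysis would show it. Whether the new scanner has closed the gap would be left to a breakdown devised after the event.

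**Working it through.** **1. Does anything else in the plan answer the hypothesis in patients?**
- Aim 2 does study microcalcifications, through "human observer performance studies on phantoms containing microcalcifications". Its purpose is to optimise reconstruction, it uses no patients, and it names no mammography comparator.
- Aim 5 compares contrast-enhanced bCT with MRI. Its location-specific data are listed for Aim 5 only, and location does not record lesion type.
- The secondary endpoint in section 6 is "the comparison of breast MRI versus breast CT in terms of sensitivity and specificity".
- Section 8 sets no calcification quota, lesion class, margin or separate power.

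So nothing else does.

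**2. The plan's own figure.** The 82% power can be neither confirmed nor refuted, because alpha, sidedness and the variance components are not given. Two assumed sets of components, at two-sided 0.05, give 80% and 91% analytically and 88% and 95% by simulation. A figure of 82% is therefore plausible. The mismatch itself does not depend on it.

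**3. Can an overall gain hide a deficit?** With common negatives and two exclusive classes of cancer, the reader-averaged empirical AUC difference is

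overall = f × d_calc + (1 − f) × d_other,

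where f is the calcification share (approximate for fitted curves). Set overall = +0.05 and assume d_calc = −0.05. Then d_other = (0.05 + 0.05f)/(1 − f):

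| f (assumed) | d_other needed |
|---|---|
| 1/5 | +0.075 |
| 1/4 | +0.083 |
| 1/3 | +0.100 |
| 1/2 | +0.150 |

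The plan gives neither f nor any lesion-specific AUC. The table shows that masking is possible, not that it is likely. The last row is extreme: from an assumed mammography AUC of 0.825 on those cancers it would need 0.975 on bCT.

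**4. How precise would a calcification subset be?** The standard error (SE) implied by 82% power for 0.05 is:
- two-sided 0.05: 0.05/(1.960 + 0.915) = 0.0174
- one-sided 0.05: 0.05/(1.645 + 0.915) = 0.0195

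Scale this by the square root of the ratio of single-AUC variances, with m positives, n = 250 negatives and A = 0.85:

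Var = [A(1 − A) + (m − 1)a + (n − 1)b]/(mn), with A(1 − A) = 0.1275.

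- Hanley-McNeil: a = A/(2 − A) − A² = 0.0166 and b = 2A²/(1 + A) − A² = 0.0586.
- Equal-variance binormal: a = b ≈ 0.0352.

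Hanley-McNeil example: m = 150 gives (0.1275 + 149 × 0.0166 + 249 × 0.0586)/37,500 = 0.000458. For m = 30 it is (0.1275 + 29 × 0.0166 + 249 × 0.0586)/7,500 = 0.00203. The ratio is 4.42, so SE = 0.0174 × √4.42 = 0.0366 and the half-width is 1.96 × 0.0366 = 0.072.

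95% CI half-widths, by how the study was sized:

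| Calcification cancers (assumed) | Hanley-McNeil ratio | two-sided | one-sided | Binormal ratio | two-sided | one-sided |
|---|---|---|---|---|---|---|
| 30 | 4.42 | 0.072 | 0.080 | 3.51 | 0.064 | 0.072 |
| 50 | 2.71 | 0.056 | 0.063 | 2.25 | 0.051 | 0.057 |
| 75 | 1.85 | 0.046 | 0.052 | 1.63 | 0.043 | 0.049 |

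The chance that the CI excludes zero is Φ(|d|/SE − 1.96). Under Hanley-McNeil with two-sided sizing, a true −0.05 gives 28%, 42% and 56% for 30, 50 and 75 cancers, and a true −0.10 gives 78%, 94% and 99%. Binormal scaling raises the first set to about 34%, 48% and 62%. One-sided sizing lowers the Hanley-McNeil figures to about 23%, 34% and 47%.

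**The case against.** The strongest reply is that the sentence is rationale. It closes a short explanation: masses already better, calcifications formerly worse, scanner now sharper. The Aim 4 heading, the general objective, the closing expectation about screening and the sample size all concern overall detection, for which an ROC comparison over all lesions is the natural test. No listed endpoint or success rule depends on the sentence. The mammography and biopsy reports are retained, and the reads come at least 6 months after imaging, so a breakdown could still be added in time.

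Most of this stands. A reader might infer that the overall AUC is the wrong test for Aim 4; the documents do not support that. A reader might also infer that a positive overall AUC will be presented as evidence on microcalcifications; no section says so. Nor do the documents show that a deficit persists on the new scanner.

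What remains is that the sentence is written as a hypothesis and the plan leaves it unanswered in patients. Rewording alone would remove the inconsistency but leave the question open. The precision figures are indeed dependent on the variance model, which is why a range is given.

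**Conclusion.** The point holds in a limited form. The overall ROC comparison is appropriate for the Aim 4 heading and the screening claim, but it does not answer the microcalcification hypothesis, and no other analysis in the documents does so in patients. Given the earlier results by lesion type, an overall gain of 0.05 could coexist with a calcification deficit.

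The size of any masking cannot be derived from the plan. A subset of 30 to 75 calcification cancers would give a 95% CI half-width of roughly 0.04 to 0.08. That can reveal a large deficit but could easily miss one of 0.05. These figures assume the number of calcification cancers, alpha 0.05, an AUC near 0.85 in the subset, and reader and modality correlations that carry over. The subset would be less precise if calcification-only cancers are fewer than 30.

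**What to change.** Keep overall AUC as the Aim 4 test. In Specific Aim 4 and in the section 8 paragraph on numbers of patients, pre-specify a descriptive breakdown of the planned reads:

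- Before reader scores are analysed, someone who is not a study reader classifies each positive from the existing mammography and pathology reports. The classes are calcification-only; mass or other finding with calcification; and no calcification.
- Calcification-only is the main group for the hypothesis, because a cancer with both features can be detected through the mass.
- Report the reader-averaged AUC difference with 95% CI for each class against the common negatives, versus 2D and versus 2D+3D.
- State that a positive overall AUC does not by itself support the microcalcification hypothesis, and that the subset result is an estimate, not a confirmatory test.
- State the limits. Enrolment on a mammographic finding (section 4) tends to favour mammography. Benign calcifications among the negatives mean that the subset AUC does not fully isolate calcification detection. Because bCT is not used for diagnosis (section 13), the lesion class rests on the other reports.

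If the sentence is meant only as rationale, also reword it so and state the Aim 4 hypothesis for overall detection.

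The cost is wording in two places, classification of about 150 positives from retained records, and one stratified analysis. No extra patients or reads are needed. The downside is the imprecision shown above.

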**Specific Aim 5: High Risk Screening Performance: CE breast CT and CE-breast MRI.**  
To evaluate the potential of CE-bCT for use in high risk screening (as MRI is used now), CE-bCT ROC performance will be compared against CE-MRI ROC performance. Radiologists will perform full 3D search of the CT and MRI (independently) volume data sets (both with and without contrast) and report

overall probability of malignancy for each modality. Location-specific metrics for potential FROC or LROC analysis will also be captured. Assessment of  $\Delta$ HU will also be performed to quantitatively evaluate predictive performance for malignancy.

Specific Aims 1 and 2 do not require changes in hardware; these two aims are completely focused on post-acquisition image processing techniques (software). Therefore, accrual to the clinical trials as described in Aim 3 can commence on day one of this project. The acquired projection image data from the scanner is always saved, and once the scatter-correction and flat fielding techniques (Aim 1) and optimized reconstruction methods (Aim 2) are finalized, images will be re-reconstructed and become available for the ROC studies on normal-risk screening (Aim 4) and high-risk screening (Aim 5) performance. We believe that this 5 year study will demonstrate that non-contrast bCT can outperform 2D & 3D mammography in breast cancer screening for normal risk patients, and that CE-bCT is (at least) equivalent to CE-MRI for screening high-risk women.

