#### 4) Inclusion and Exclusion Criteria

##### Inclusion Criteria:

- Age at least 35 years old
- Diagnostic findings from prior mammography highly suggestive of breast malignancy (BI-RADS® category 4 or BI-RADS® category 5)
- Not pregnant or breast-feeding
- Ability to lay still and hold breath for approximately 15 seconds

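### Aim 5 draws a conclusion about high-risk screening from women enrolled only for BI-RADS 4 or 5 mammograms and going to biopsy

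*Combined protocol and SAP*

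**What the plan says.** Section 2 (Objectives) opens Aim 5 cautiously: "To evaluate the potential of CE-bCT for use in high risk screening (as MRI is used now"). The paragraph that closes the specific aims goes further. It states the belief that the five-year study will demonstrate that "CE-bCT is (at least) equivalent to CE-MRI for screening high-risk women", alongside a similar expectation that non-contrast breast CT will outperform mammography in normal-risk screening (Aim 4).

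The study population is described in three places:

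- Specific Aim 3 plans one pool of 400 women for both aims, described as those "whose images will be used for the normal-risk patient screening comparisons (Aim 4) and for the high risk patient screening comparisons (Aim 5").
- Section 8 states: "All cases will be recruited from BIRADS 4 & 5 women who will be biopsied in our facility".
- Section 4 requires "Diagnostic findings from prior mammography highly suggestive of breast malignancy", meaning BI-RADS category 4 or 5. The checklist in Appendix 2 repeats this.

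Neither list mentions genetic status, family history or a risk score. Section 8 sizes Aim 5 with 4 readers and 150 cases (60 positive, 90 negative), and counts breast CT as successful if the observed difference in reader-averaged AUC (CT minus MRI) exceeds -0.025. It calls this a pilot study. Section 6 lists the MRI-CT comparison as a secondary endpoint judged against biopsy and names no screening population.

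**The concern.** The stated conclusion is about one population and the data come from another. A high-risk woman screened with MRI may well have an unremarkable mammogram, and this design gives such a woman no way in. Some enrolled women may happen to be at high risk, but the plan neither identifies nor counts them.

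If the plan is followed exactly and the success rule is met, the result supports a statement about biopsy-bound women with a suspicious mammogram. Reporting it as equivalence for high-risk screening would carry it to women and cancers that the study did not set out to sample, in a setting where the choice between MRI and CT matters.

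**Working it through.** **1. The plan's recruitment figures (section 8).** The inputs are 480 biopsies a year, four years of recruitment, "we assume the historical 38% positive biopsy rate for our facility", and the target "the minimum number of women we need to recruit to run the study is 150 with biopsy-verified cancer". The projection is introduced by "Given a total of 1,920 candidate women, the 38% positive rate for biopsy, and a 25% rate of recruitment".

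- Total needed: 150 / 0.38 = 394.7, rounded in the plan to 400.
- Candidates: 480 × 4 = 1,920.
- Recruited: 1,920 × 0.25 = 480.
- Expected cancers: 480 × 0.38 = 182.4 (plan: 182).
- Expected benign: 480 × 0.62 = 297.6 (plan: about 298).

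All of these reproduce. They also show that every recruited woman is counted out of the biopsy stream; no other source of cases feeds Aim 5.

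**2. How selected the pool is.** Cancers make up 38% of the expected pool and 60 / 150 = 40% of the Aim 5 reading set. From the facility's own volumes, positive biopsies per screen are about 480 × 0.38 / 15,818 = 182.4 / 15,818 = 1.15%. This is rough, because not every biopsy follows a screen and these screens are not specifically of high-risk women. The gap does not itself distort AUC, which is unaffected by prevalence. It shows only how far the pool is from a screening population.

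**3. Why the case mix still matters.** AUC is the probability that a randomly chosen cancer is rated above a randomly chosen non-cancer. Let q be the share of cancers in the target population that mammography does not show. With the same non-cancers throughout, the CT-minus-MRI difference in the target population is

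D(target) = (1 − q) × D(visible) + q × D(occult).

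The trial is designed to estimate essentially D(visible). The documents give neither q nor D(occult), not even the sign of D(occult). The non-cancers would change as well: women with a benign biopsy after a suspicious mammogram are not the negatives met in screening. D(target) therefore cannot be recovered from the planned data, and it could lie on either side of D(visible).

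**4. Whether anything else in the plan supplies the missing population.**

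- Eligibility (section 4, Appendix 2): no risk criterion.
- Analysis (section 8): no risk variable, stratum or subgroup.
- Unaffected breasts (section 8): offered as normal images for Aim 4 only.
- Endpoint (section 6): MRI against CT with biopsy as reference, and no risk claim.

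Nothing restricts the closing conclusion to women with a mammographic abnormality, and nothing brings in women without one.

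**The case against.** The best defence is that the plan does not formally claim what is criticised. The closing sentence is a belief in the style of a grant application. Aim 5 itself speaks of potential, section 8 speaks of a pilot, and the formal endpoint in section 6 is silent on high-risk screening. No success rule or case count depends on the sentence. All of that is true, and it is why this is a matter of wording. But none of those qualifiers changes the population named: Specific Aim 3 and the closing paragraph both refer to high-risk screening, and no text limits the inference.

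A second defence also stands. The normal-risk and high-risk labels can be read as names for intended applications: Specific Aim 2 explains that contrast injection is impractical for screening normal-risk women. The labels do not assert that the same women belong to both risk groups, and they can stay.

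A reader might infer more than the documents support, in three ways:

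- *That selection by mammography favours CT because both use x-rays.* This is not shown. Section 3 attributes mammography's difficulty in dense breasts to overlapping structures in a projection image, which tomography reduces, and reports that masses are seen better on contrast-enhanced breast CT than on mammography. A cancer hidden on a mammogram need not be hidden on CT.
- *That the study says nothing about cancers mammography misses.* This is too strong. Both breasts are imaged with both modalities, and readers search the full volumes, so such cancers may turn up incidentally. They are simply not sampled by design.
- *That the -0.025 margin would be breached in high-risk women.* With D(visible) = 0 and an assumed D(occult) of -0.10, the formula gives -0.02, -0.03 and -0.05 at q = 20%, 30% and 50%. These are products of two assumed values, the first does not cross the margin, and a positive D(occult) would reverse the sign. They are not evidence of a deficit.

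**Conclusion.** The concern holds as a limit on the conclusion. As designed, Aim 5 can support a statement about contrast-enhanced breast CT against contrast-enhanced MRI in women with BI-RADS 4 or 5 mammographic findings going to biopsy. It cannot support the stated conclusion about screening high-risk women. This rests on the eligibility and recruitment text and on the dependence of AUC on case mix; it needs no assumed figure. The direction and size of any difference in a high-risk screening population are unknown from these documents.

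The paired comparison itself remains valid in the enrolled population, and the case numbers and planned analyses are unaffected. The normal-risk conclusion of Aim 4 has the same limit, eased only partly by the unaffected breasts used as normals, because its cancers come from the same pool.

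**What to change.** Make three wording changes, in Specific Aims 3 and 5, the closing paragraph of the aims, and the Aim 5 sizing text in section 8:

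1. State the Aim 5 conclusion as non-inferiority of contrast-enhanced breast CT to contrast-enhanced MRI in women with BI-RADS 4 or 5 mammographic findings going to biopsy.
2. Describe high-risk screening only as a possible future application that would need a study of its own.
3. In the closing paragraph, apply the same population limit to the normal-risk screening conclusion of Aim 4.

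This brings the aims into line with the secondary endpoint in section 6. It needs no change to recruitment, imaging, reading or sample size. The cost is a narrower claim.

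A high-risk subgroup table is not proposed as a substitute. Section 8 lists medical history without saying what risk information it holds, and the documents define no high-risk category. If an assumed 2% to 20% of women were at high risk, only about 1 to 12 of the 60 Aim 5 cancers would be theirs (60 × 0.02 = 1.2; 60 × 0.20 = 12).
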